4.5.4. Pregnancies

While pregnancy itself is not considered to be an AE or SAE, any pregnancy complication or elective termination of a pregnancy for medical reasons will be recorded as an AE or SAE as described in the protocol. If participants become pregnant while on the study, or the female partner of a male participant becomes pregnant during the study, the information will be included in the narratives and no separate table or listing will be produced.

4.5.5. Additional Safety Assessments

Laboratory evaluations including the analyses of chemistry, hematology, coagulation, cardiac function, thyroid function and routine urinalysis laboratory tests and other screening tests will be based on GSK Core Data Standards.

Unless otherwise specified, the denominator in percentage calculation at each scheduled visit will be based on the number of participants with non-missing value at each particular visit.

4.5.5.1. Laboratory Data

The assessment of laboratory toxicities will examine the laboratory tests listed in Appendix 2 in the protocol. Laboratory grades will be evaluated using CTCAE v5.0. However, some tests are not graded using CTCAE. For hematology, Red Blood Cell (RBC) is not gradable by CTCAE v5.0. For clinical chemistry, BUN and creatinine clearance are not gradable by CTCAE v5.0. For sodium, potassium, calcium, glucose, and magnesium there will be two bi-directional parameters (hyper and hypo) created and the tests will be graded by CTCAE v5.0 in both directions.

Summaries of worst-case grade increase from baseline grade will be provided for all the chemistry, hematology, coagulation and thyroid function lab tests that are gradable by CTCAE v5.0. These summaries will display the number and percentage of participants with a maximum post-baseline grade increasing from their baseline grade. Any increase in grade from baseline will be summarized along with any increase to a maximum grade of 3 and any increase to a maximum grade of 4. Missing baseline grade will be assumed as grade 0. For laboratory tests that are graded for both low and high values, summaries

will be done separately and labelled by direction, e.g., sodium will be summarized as hyponatremia and hypernatremia separately.

Liver function laboratory tests will be included with chemistry lab tests. A listing of liver monitoring/stopping events will also be produced, where appropriate.

A listing of all laboratory data and urinalysis data will be produced, separately.

Hepatobiliary laboratory events including possible Hy's law cases will be listed, in addition to what has been described above. Possible Hy's law cases are defined as any elevated alanine aminotransferase (ALT) $\geq 3 \times$ upper limit of normal (ULN) and total bilirubin $\geq 2 \times$ ULN, or ALT $\geq 3 \times$ ULN and INR > 1.5 . Hy's law cases where ALT $\geq 3 \times$ ULN and total bilirubin $\geq 2 \times$ ULN, with alkaline phosphatase (ALP) $< 2 \times$ ULN at the time of bilirubin elevation will also be considered. Total bilirubin $\geq 2 \times$ ULN can be within 28 days following the ALT elevation and if direct bilirubin is available on the same day, it must be $> 35\%$ of total bilirubin.

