5.1. Inclusion Criteria

Participants are eligible for inclusion in this study if all the following criteria apply:

1. Capable of giving signed informed consent/assent which includes compliance with the requirements and restrictions listed in the ICF and in this protocol
2. Male or female, age ≥ 18 years; at the time consent is obtained (minimum age requirement per local regulatory requirements)
3. Histological or cytological documentation of HNSCC that was diagnosed as recurrent or metastatic and considered incurable by local therapies
4. Primary tumor location of the oral cavity, oropharynx, hypopharynx or larynx
5. No prior systemic therapy administered in the recurrent or metastatic setting (with the exception of systemic therapy completed > 6 months prior if given as part of multimodal treatment for locally advanced disease and no disease progression/recurrence within 6 months of the completion of curatively intended systemic treatment)
6. Measurable disease per response evaluation criteria in solid tumors (RECIST) version 1.1 guidelines
7. Eastern Cooperative Oncology Group (ECOG) Performance Status (PS) score of 0 or 1
8. Adequate organ function as defined in [Table 3](#).

Table 3 Definitions of Adequate Organ Function

System	Laboratory Values
Hematologic^{a,b}	
ANC	$\geq 1.5 \times 10^9/L$
Hemoglobin	≥ 9 g/dL
Platelets	$\geq 100 \times 10^9/L$
Hepatic^b	
Albumin	≥ 2.5 g/dL
ALT	$\leq 2.5 \times ULN$ or $\leq 5 \times ULN$ for participants with documented liver metastases
Total bilirubin	Bilirubin $\leq 1.5 \times ULN$ (isolated bilirubin $> 1.5 \times ULN$ is acceptable if bilirubin is fractionated and direct bilirubin $< 35\%$)
Renal^b	
Calculated CrCl ^c	≥ 60 mL/min

System	Laboratory Values
Coagulation^b	
INR OR PT aPTT	$\leq 1.5 \times \text{ULN}$ unless participant is receiving anticoagulant therapy as long as PT or aPTT is within therapeutic range of intended use of anticoagulants
Cardiac^b	
Ejection fraction ^d	$\geq 50\%$

Abbreviations: ANC = Absolute neutrophil count; ALT = alanine aminotransferase; CrCl = creatinine clearance; ECHO= echocardiogram; eGFR=estimated glomerular filtration rate; MUGA= multigated acquisition scan TSH = thyroid-stimulating hormone; ULN = upper limit of normal; WNL = within normal limits

- Participants may be transfused or receive growth factor treatment to meet minimum hematologic values up to 7 days prior to determining eligibility

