8.3.7. Events of Clinical Interest

Selected events that may be non-serious or serious adverse events and are considered as Events of Clinical Interest (ECI) in this study protocol and must be reported to the Sponsor.

Events of clinical interest include:

1. An overdose of Study Treatment (GSK3359609/Pembrolizumab), as defined in Section 8.4 that is not associated with clinical symptoms or abnormal laboratory results.
2. An elevated AST (aspartate aminotransferase) or ALT (alanine aminotransferase) lab value that is greater than or equal to 3X the upper limit of normal and an elevated total bilirubin lab value that is greater than or equal to 2X the upper limit of normal and, at the same time, an alkaline phosphatase lab value that is less than 2X the upper limit of normal, as determined by way of protocol-specified laboratory testing or unscheduled laboratory testing.*

*Note: These criteria are based upon available regulatory guidance documents. The purpose of the criteria is to specify a threshold of abnormal hepatic tests that may require an additional evaluation for an underlying etiology. The study site guidance for assessment and follow up of these criteria can be made available. It may also be appropriate to conduct additional evaluation for an underlying etiology in the setting of abnormalities of liver blood tests including AST, ALT, bilirubin, and alkaline

phosphatase that do not meet the criteria noted above. In these cases, the decision to proceed with additional evaluation will be made through consultation between the study investigators and the GSK Medical Monitor. However, abnormalities of liver blood tests that do not meet the criteria noted above are not ECIs for this study.

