
INR) and perform liver event follow up assessments within 24 hours
 
 • Monitor participant twice weekly until liver chemistries resolve, stabilize or return to within baseline • A specialist or hepatology consultation is recommended 
For All other criteria:
 
 • Repeat liver chemistries (include ALT, AST, alkaline phosphatase, bilirubin and INR) and perform liver event follow up assessments within 24-72 hours • Monitor participant weekly until liver chemistries resolve, stabilize or return to within baseline 	
quantitative total immunoglobulin G (IgG or gamma globulins)
 
 • Serum acetaminophen adduct HPLC assay (quantifies potential acetaminophen contribution to liver injury in participants with definite or likely acetaminophen use in the preceding week [James, 2009]). NOTE: not required in China • Liver imaging (ultrasound, magnetic resonance, or computerized tomography) and /or liver biopsy to evaluate liver disease; complete Liver Imaging and/or Liver Biopsy CRF forms
---	--

1. Serum bilirubin fractionation should be performed if testing is available. If serum bilirubin fractionation is not immediately available, discontinue study drug(s) for that participant if ALT \geq 3xULN **and** bilirubin \geq 2xULN. Additionally, if serum bilirubin fractionation testing is unavailable, **record presence of detectable urinary bilirubin on dipstick**, indicating direct bilirubin elevations and suggesting liver injury
2. All events of ALT \geq 3xULN **and** bilirubin \geq 2xULN (>35% direct bilirubin) or ALT \geq 3xULN **and** INR>1.5, which may indicate severe liver injury (possible ‘Hy’s Law’), **must be reported as an SAE (excluding studies of hepatic impairment or cirrhosis)**; the INR threshold value stated will not apply to participants receiving anticoagulants
3. New or worsening symptoms believed to be related to liver injury (such as fatigue, nausea, vomiting, right upper quadrant pain or tenderness, or jaundice) or believed to be related to hypersensitivity (such as fever, rash or eosinophilia)
4. Study drugs refer to all drugs that comprise a study treatment arm. Refer to the central laboratory manual for instructions on sample requirements for follow-up tests performed at central laboratory.

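### The SAP's possible-Hy's-law rule applies INR >1.5 without the protocol's exemption for participants receiving anticoagulants

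*SAP*

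**What the plan says.** SAP Section 4.5.5.1 plans a listing introduced as "Hepatobiliary laboratory events including possible" Hy's law cases. Possible Hy's "law cases are defined as any elevated alanine aminotransferase (ALT") at ≥3×ULN with total bilirubin ≥2×ULN, or ALT ≥3×ULN with INR >1.5. A further sentence covers the ALT and bilirubin pattern "with alkaline phosphatase (ALP") below 2×ULN. Bilirubin may follow the ALT rise by up to 28 days and, where direct bilirubin is available the same day, it must exceed 35% of the total. Nothing is said about anticoagulants.

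Protocol Section 10.8 (Appendix 8), Table 17, footnote 2, holds the protocol's own possible-Hy's-law definition: ALT ≥3×ULN with bilirubin ≥2×ULN (more than 35% direct), or ALT ≥3×ULN with INR >1.5. Such events must be reported as SAEs. The footnote ends with the exemption that "the INR threshold value stated will not apply to participants receiving anticoagulants".

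Protocol Section 5.1, Table 3, limits INR, PT and aPTT at entry "unless participant is receiving anticoagulant therapy as long as PT or aPTT is within therapeutic range of intended use of anticoagulants".

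**The concern.** The SAP reuses the protocol's INR cut-off but leaves out the qualifier attached to it. It does carry over the footnote's other qualifier, the 35% direct-bilirubin condition, in modified form. SAP Section 1.1, which lists changes from the protocol's planned analysis, does not mention the anticoagulant exemption. This looks like an omission, not a decision.

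In an anticoagulated participant, INR reflects the drug as well as the liver, so INR >1.5 is not by itself a sign of liver injury. Two things are at stake. The listing can contain people whom the protocol does not class as possible Hy's law cases on that criterion. It can also disagree with the SAE data, because footnote 2 makes a qualifying event a mandatory SAE and an exempt participant generates none under the INR criterion. Under SAP Section 1.1 the report is abbreviated, with minimal safety analyses and no between-treatment safety comparison, so readers will rely more on individual flagged liver cases.

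**Working it through.** No figure in the plan depends on this point, so the check sets the two rules side by side and applies them to example laboratory profiles.

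**Rules**

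- SAP 4.5.5.1: ALT ≥3×ULN and (bilirubin ≥2×ULN or INR >1.5).
- Protocol Table 17, footnote 2: ALT ≥3×ULN and (bilirubin ≥2×ULN with >35% direct, or INR >1.5 if not receiving an anticoagulant).

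**Profiles (hypothetical)**

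| Profile | SAP possible Hy's law | Protocol possible Hy's law |
|---|---|---|
| A. On an anticoagulant; ALT 3.2×ULN, bilirubin 0.8×ULN, INR 2.5 | Yes, INR arm | No: INR threshold does not apply, and 0.8 <2 |
| A with the same values, no anticoagulant | Yes, INR arm | Yes, INR arm |
| B. AST 4×ULN, ALT 2×ULN, bilirubin 2.5×ULN, ALP 1×ULN | No, 2 <3 | No, 2 <3 |

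Only profile A separates the two rules, and the difference is entirely the missing exemption. Profile B shows that they agree on which transaminase counts.

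**Can profile A occur in this trial?**

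1. Protocol Table 3 admits anticoagulated participants.
2. Protocol Table 2 names raised INR with warfarin among the 5FU risks, and 5FU is planned in both arms for 6 cycles.
3. The Schedule of Activities repeats coagulation tests every 3 weeks on treatment, and Table 15 lists INR or PT among them.
4. Protocol Table 6 includes ALT elevation among the immune-related events to be managed.

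The combination is possible. How often it occurs is a product of three proportions: receiving an anticoagulant; reaching ALT ≥3×ULN given that; and having INR >1.5 given both. The documents give none of the three.

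**The case against.** The strongest reply is that little depends on this listing. It shows possible cases participant by participant for medical review; it is neither an adjudicated count nor a test. The SAP also states that "A listing of liver monitoring/stopping events will also be produced, where appropriate", and Tables 17 and 18 define those events with the exemption in place, so a reader could compare the two listings. Programming detail sits in the Output and Programming Specification (OPS), which is not available here and may already contain the exemption. Most of this stands: it limits the consequence and rules out saying that the listing will contain wrong cases. It does not remove the discrepancy, because the SAP text is the stated definition and it differs from the protocol's.

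Two stronger readings are tempting, and the documents do not support them.

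- **That the ALT-only rule misses protocol-defined Hy's law cases.** Protocol Section 8.3.7 does use "An elevated AST (aspartate aminotransferase) or ALT (alanine aminotransferase) lab value that is greater than or equal to 3X the upper limit" of normal, with bilirubin ≥2×ULN and, at the same time, ALP <2×ULN. That is a separate event of clinical interest, which 8.3.7 does not call Hy's law. The protocol's own Hy's law definition is ALT only, as are Tables 17 and 18, so the SAP matches it. Nor can one say that an AST-only event goes unlisted. The hepatobiliary listing is wider than Hy's law cases, and "A listing of all laboratory data and urinalysis data will be produced, separately".
- **That false cases could be numerous enough to change the hepatic conclusion.** Assuming 5–15% anticoagulated and 3–10% of those reaching ALT ≥3×ULN gives 5% × 3% = 0.15% to 15% × 10% = 1.5% of participants. Neither input comes from the documents. The product also sets the third proportion to 100%, although Table 3 refers to PT or aPTT in therapeutic range and does not imply INR >1.5 for everyone. Given those inputs it is a ceiling, not an estimate.

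A participant in profile A also cannot be said to have normal liver function. The INR is simply uninformative on that question.

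**Conclusion.** The point holds for the INR arm. SAP Section 4.5.5.1 and Protocol Table 17, footnote 2, give different answers for an anticoagulated participant with ALT ≥3×ULN, INR >1.5 and bilirubin below 2×ULN. The SAP would list that person as a possible Hy's law case; the protocol's INR criterion would not, and would not require an SAE report on that basis. The effect on the report requires at least one such participant, and that the OPS follows the SAP text as written. The number cannot be sized from the documents. The consequence is confined to a descriptive safety listing and its agreement with the SAE data. On choice of transaminase the SAP's Hy's law rule agrees with the protocol's and needs no change.

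**What to change.** Reconcile SAP Section 4.5.5.1 with Protocol Table 17, footnote 2, in one of two ways:

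1. Apply the INR >1.5 arm only to participants not receiving an anticoagulant at the time, identified from concomitant medication data; or
2. Keep such participants in the listing but flag anticoagulant use, so that they can be told apart from cases meeting the protocol definition.

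Either version should state what counts as receiving an anticoagulant at the time, for example on the date of the INR sample. The second keeps the cases visible to a medical reviewer, which suits an INR that is uninformative.

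The cost is a one-line SAP edit and a matching change to the OPS derivation. Protocol Section 6.5 already requires concomitant medications with start and end dates, and INR or PT is already in the laboratory panel. This changes how cases are classified in the report and leaves the protocol's liver stopping criteria untouched.

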4.5.5.2. Vital Signs

Summaries of grade increase in systolic blood pressure (SBP) and diastolic blood pressure (DBP) will be not be produced.

4.5.5.3. ECG

A 12-lead ECG will be performed at Screening to calculate the heart rate and measurements such as PR, QRS, and QT intervals. ECG after Screening will be performed as clinically indicated. Data will not be summarized.

4.5.5.4. Performance Status

ECOG performance status will be summarized at baseline only, for the mITT Analysis Set.

4.6. Other Analyses

4.6.1. Blinded Independent Central Review (BICR) Auditing Plan

Due to early study termination, no BICR will be performed as planned. Refer to [Appendix 5](#): BICR Implementation Plan.

4.7. Interim Analyses

The Independent Data Monitoring Committee (IDMC) will make recommendations for discontinuation or modification of the study based on ongoing reviews of safety data according to the IDMC Charter. In addition, the IDMC will also evaluate all adaptive decision analyses, PFS analysis and OS interim analysis, and make recommendations based on observed results of the study and the totality of the data available.

If the study continues as a phase III, there will be two interim analyses on OS, allowing for early stopping of the study due to efficacy or allow for non-binding futility analysis.

For the Phase III study with no enrollment pause, the timing of the two interim analyses will be triggered by the pre-specified number of OS events in the total population. The final analysis of PFS will be aligned with the first OS interim analysis.

For the Phase II/III study with an enrollment pause, the first interim analyses of OS (IA1, adaptive decision making) will occur when the first 300 participants have a minimum follow-up of 9 months. A futility criterion of $p\text{-value} > 0.1$ for log-rank test of OS is pre-specified for adaptive decision making. If the futility criterion is not met at the first interim analysis (IA1), the study will continue as a Phase III study and enrollment of an additional 340 participants to a total of 640 participants will occur. If the futility criterion is met in the OS analysis, the study will stop for futility. The timing of the second interim analyses will be triggered by the pre-specified number of OS events in the total population. The final analysis of PFS will be aligned with the second OS interim analysis.

The nominal significance levels for the interim and final analyses of OS will be determined by the Lan-DeMets spending function based upon the O'Brien-Fleming boundary. The futility bounds of this study are non-binding and the bounds are considered guidance rather than strict bounds.

Table 5 and Table 6 summarize the required number of events, sample size and decision guidance for the planned PFS and OS analyses for the two Phase III study scenarios, respectively. Efficacy boundaries and non-binding futility boundaries are based on initially assigned type I error rate before any alpha re-allocation and projected number of events at study milestones. The actual boundaries will be determined from the actual number of interim analyses conducted and from the actual number of events, at the time of the specified interim analysis using the alpha- and beta- spending functions. Actual futility bounds will be updated if overall beta is changed with respect to alpha reallocation.

Results of the interim analyses will be reviewed by an independent data monitoring committee (IDMC). Further details of interim analyses are provided in the IDMC Charter. Any change to the planned event size will be described in the statistical analysis plan before any unblinding of the data except in the event of early study termination.

Due to early study termination, no interim analyses will be performed.

Table 5 Summary of Number of Events, Sample Size and Decision Guidance at the Planned Interim and Final Analyses for Phase III Study with no Pause in Enrollment

Analysis	Key Endpts	Expected Number of Events at the Planned Analysis (Information Fraction)	Efficacy Boundary ¹		Non-binding Futility Boundary ¹	
			p-value	Cumulative Alpha	p-value	Cumulative Beta
IA1 : Final PFS Analysis (H3, H4), Interim OS Analysis 1 (H1, H2)	PFS	~470 (100%)	0.0001	0.0001	NA	NA
	OS	~310 (76%)	0.01	0.01	0.619	0.0007
IA2 : Interim OS Analysis 2 (H1, H2)	OS	~375 (92%)	0.0016	0.019	0.143	0.017
FA : Final OS Analysis (H1, H2)	OS	~410 (100%)	0.019	0.0249	0.019	0.094

Abbreviations: Endpts=endpoints; FA: final analysis; H=hypothesis; IA: interim analysis; NA: not applicable; PFS=progression-free survival; OS=overall survival

1. Efficacy boundaries and non-binding futility boundaries are based on initially assigned type I error rate (one-sided) before any alpha roll-over and projected number of events at study milestones. Actual efficacy boundaries will be based on the actual number of interim analyses conducted and actual numbers of events available at study milestones. Actual futility bounds will be updated if overall beta is changed with respect to alpha roll-over.
2. The timing of interim analyses and final analysis for OS may be delayed in the presence of non-proportional hazards.

Table 6 Summary of Number of Events, Sample Size and Decision Guidance at the Planned Interim and Final Analyses for Phase II/III Study with Pause in Enrollment

Analysis	Key Endpts	Expected Number of Events at the Planned Analysis (Information Fraction)	Efficacy Boundary ¹		Non-binding Futility Boundary ¹	
			p-value	Cumulative Alpha	p-value	Cumulative Beta
IA1 : Interim OS Analysis ^{1, 3} (H1, H2)	OS	~136 (32%)	0.00007	0.00007	0.1	0.263
IA2 : Final PFS Analysis (H3, H4); Interim OS Analysis ² (H1, H2)	PFS	~456 (100%)	0.0001	0.0001	NA	NA
	OS	~315 (74%)	0.009	0.009	NA	0.263
FA : Final OS Analysis (H1, H2)	OS	~425 (100%)	0.022	0.0249	0.022	0.288

Abbreviations: Endpts=endpoints; FA: final analysis; H=hypothesis; IA: interim analysis; NA: not applicable; PFS=progression-free survival; OS=overall survival

1. Efficacy boundaries and non-binding futility boundaries are based on initially assigned type I error rate before any alpha roll-over and projected number of events at study milestones. Actual efficacy boundaries will be based on the actual number of interim analyses conducted and actual numbers of events available at study milestones. Actual futility bounds will be updated if overall beta is changed with respect to alpha roll-over.
2. The timing of interim analyses and final analysis for OS may be delayed in the presence of non-proportional hazards.
3. Represents the OS adaptive decision analysis timepoint. If OS reaches the futility boundary then no further OS analyses will be performed and IA1 becomes the end of Phase II for OS.

